3.7.3 Adverse Events

All AEs will be coded and summarized using the Medical Dictionary for Regulatory Activities (MedDRA) (version 23.1). Treatment-emergent AEs (TEAEs) are defined as any new or worsening events reported at any time from the date of first dose of study medication until the end of study participation. All AEs will be presented in by-subject data listings, including the verbatim and coded terms, onset day (relative to start of treatment), severity, relationship to study medication, action taken, and outcome.

An overview of AEs for the SS will be provided, summarizing the frequency/incidence of the following:

- Incidence of all AEs;
- Count of TEAEs;
- Incidence of TEAEs;
- Count of Treatment-emergent SAEs (TESAEs);
- Incidence of TESAEs;
- Incidence of TEAE by maximum severity;
- Incidence of TESAE by maximum severity;
- Incidence of TEAEs that lead to discontinuation of study treatment;
- Incidence of TESAEs that lead to discontinuation of study treatment;
- Incidence of TEAEs that lead to interruption of study treatment;
- Incidence of TESAEs that lead to interruption of study treatment;
- Incidence of Treatment-related TEAEs;
- Incidence of Treatment-related TESAEs.

The number and percentage of subjects with AEs will also be summarized by System Organ Class (SOC) and Preferred Term (PT) for the following categories:

- Incidence of TEAEs;
- Incidence of TESAEs;
- Incidence of TEAEs by maximum severity;

- Incidence of TEAEs that lead to discontinuation from study treatment;
- Incidence of TEAEs that lead to interruption from study treatment;
- Incidence of Treatment-related TEAEs.

3.7.4 Laboratory Tests

For each laboratory test, summaries will be provided for baseline and Day 29. The absolute value and its change from baseline will be descriptively presented. Abnormal laboratory observations and urinalysis microscopic exams, if performed, will be listed.

3.7.5 Physical Examinations

Physical examination results will listed.

3.7.6 Vital Signs

Vital signs measurements include pulse rate, temperature, systolic blood pressure, and diastolic blood pressure. Measures at baseline and changes from baseline to post baseline visit (Day 15, Day 29) will be summarized using descriptive statistics.

3.7.7 Electrocardiogram

Electrocardiogram results will be descriptively summarized (n, mean, Std Dev, ..., etc.) for heart rate, PR, RR, QRS, QT interval, QTcB, and QTcF by visit. In addition, number and percentage of subjects with abnormal QTcB/QTcF (ie, >450 msec, >480 msec, >500 msec) or increase of QTcB/QTcF (>30 msec, >60 msec) from screening will be provided for each visit.

3.8 PK ANALYSES

Plasma concentration of the study drug will be summarized using descriptive statistics including number of subjects with plasma samples, number of assays with concentrations above lower limit of quantification (LLOQ), arithmetic mean, geometric mean, Std Dev, coefficient of variation (CV), minimum and maximum at each nominal visit (Day 15, Day 29). A concentration that falls below the LLOQ will be treated as zero in the summary. Analysis will be conducted on PKs.

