2 INTRODUCTION

2.1 Study Rationale

TER-101 1% topical ointment was tested in a previous Phase 1/2a randomized, double-blind, vehicle-controlled, sequential group study assessing safety, tolerability, pharmacokinetics (PK), and efficacy of twice daily topical application of TER-101 1% on body surface areas (BSAs) up to 50% for up to 2 weeks in healthy volunteers (n=8) and subjects with atopic dermatitis (AD) (n=28).

The application of TER-101 (1% w/w) ointment was well tolerated by both healthy volunteers and subjects with moderate to severe AD. Absorption of TER-101 (1% w/w) ointment into the bloodstream was evident in subjects with AD, but absorption was low; while in healthy volunteers, absorption was sporadic and limited. There was no evidence of toxicity or safety concerns. In this small study, statistical evidence to conclude that there was a difference between TER-101 (1% w/w) ointment and ointment vehicle for improvement in disease severity and itching was insufficient.

This Phase 2a study will compare the higher concentration TER-101 (2.75% weight for weight [w/w]) ointment to its vehicle over a longer treatment period (ie, 4 weeks) than the prior Phase 1/2a study and will be performed in subjects aged 12 – 65 with mild or moderate AD. The proposed TER-101 2.75% dose and patient population is supported by nonclinical studies.

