5.1 Inclusion Criteria

Subjects are eligible to be included in the study only if all of the following criteria apply:

1. Adolescent or adult subject aged 12 – 65 years.
2. Able to understand and give documented informed consent if an adult/parent/guardian and able to understand and provide assent if a minor (age 12-17).
3. Diagnosis of AD according to the Hanifin and Rajka criteria [[Appendix 5, Section 10.5](#)].
4. AD disease duration of at least 6 months, with no change in treatment or severity for at least 4 weeks prior to screening.
5. Overall IGA score of 2 (mild) or 3 (moderate) at baseline on a 5-point IGA scale.

6. TBSA affected of between 2 and 30% at baseline.
7. EASI \geq 5 at baseline.

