6.1.1 Study Treatment Application

TER-101 (2.75% w/w) ointment and ointment vehicle will be applied topically twice a day for 28 days, with at least 8 hours between applications. Subjects will apply sufficient study drug to provide a thin covering. A pea-sized amount (approximately 250 mg) should cover approximately 2% BSA. Additional instructions on application will be provide in the 'Instructions for Use' provided to each subject at randomization.

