1.2 SAMPLE SIZE

The sample size is based on a clinical rather than statistical rationale. Approximately 60 subjects are planned to be enrolled and randomized, considering a potential 15% drop-out rate, to yield approximately 50 subjects completing the study.

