1.3 UNBLINDING

After all subjects complete the end of treatment visit, the database will be locked and unblinded for statistical analysis of topline results while awaiting completion of 30-day post-treatment period for all subjects. Topline summaries will be provided to the sponsor's Chief Medical Officer for planning future drug development strategies, with no impact on this study's conduct. Subject level unblinded results will not be disclosed to study subjects, investigators, or TrialSpark project team members until 30 days after the last visit of the last subjects to collect reported adverse events (AEs).

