2.4.4 Evaluations – PK

Plasma levels of TER-101 on Days 15, 29 will be analyzed and reported in a separate PK report, if topline results indicate a signal for clinical activity or before the samples exceed their stability, whichever comes first.

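### SAP 3.8 sets concentrations below the LLOQ to zero and also reports a geometric mean, which one such value makes zero or undefined

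*SAP*

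**What the plan says.** SAP 3.8 summarises plasma TER-101 at nominal Days 15 and 29. It lists the number of subjects with samples, the number of assays above the LLOQ, "arithmetic mean, geometric mean, Std Dev, coefficient of variation (CV"), minimum and maximum. It then adds: "A concentration that falls below the LLOQ will be treated as zero in the summary". The rule covers the whole summary. Protocol 8.6 and 9.4.5 and SAP section 4 do not mention values below the LLOQ.

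On expected levels, Protocol 2.1 reports that systemic absorption of the 1% ointment "was evident in subjects with AD, but absorption was low".

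On timing, SAP 1.3 says that after the last end-of-treatment visit "the database will be locked and unblinded for statistical analysis of topline results". SAP 2.4.4 sends the plasma data to a separate report, to be produced "if topline results indicate a signal for clinical activity or before the samples exceed their stability", whichever is earlier.

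On sampling, the objectives tables (Protocol section 3, SAP 1.1) and Protocol 9.4.5 call the endpoint a trough level; SAP 3.8 does not use the word. Protocol 8.6 requires only that blood be drawn 4 hours or more after the last application. Protocol 4.1.3 requires at least 8 hours between applications. The Schedule of Activities ends dosing on the evening of Day 28 and gives the final visit a window of plus or minus 3 days.

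**The concern.** The geometric mean and the zero rule cannot both be carried out once a visit has any value below the LLOQ. Systemic exposure is a stated secondary objective, and the geometric mean is one of its planned summaries.

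The programmer would then have to improvise, and the easiest step, dropping the zeros, biases the result upward. Because PK reporting is tied to the topline result or to sample stability, the choice would probably be made after unblinding.

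A related question is what the summary measures. A sample can comply with the protocol without being a trough, and SAP 3.8 would pool it with true troughs by nominal visit.

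**Working it through.** **The defect itself.** The geometric mean is (∏xᵢ)^(1/n) = exp(mean of ln xᵢ). Take 24 values of 2.0 and one value set to 0. The product form gives 0; the log form contains ln 0, so the result is 0 or missing depending on the software. The arithmetic mean is 48/25 = 1.92 and remains usable.

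**How likely it is.** SAP 1.2 plans about 60 randomised subjects "to yield approximately 50 subjects completing the study" (60 × 0.85 = 51). With 1:1 allocation that is about 25 on TER-101. The chance of at least one value below the LLOQ at a visit is 1 − (1 − f)^25, where f is the true rate, which is an assumption:
- f = 2%: 1 − 0.98^25 = 0.40
- f = 5%: 1 − 0.95^25 = 0.72
- f = 10%: 1 − 0.90^25 = 0.93

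**Size of the error by handling rule.** Assume lognormal concentrations with log-SD s. Let z be the normal quantile of f and φ the normal density at z.
- Zeros dropped: ratio to the true geometric mean = exp(sφ/(1 − f)).
- LLOQ/2 substituted: ratio = exp(sφ + f(sz − ln 2)).

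With s from 0.8 to 1.2:

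| f | z | φ | Zeros dropped / true | LLOQ/2 / true |
|---|---|---|---|---|
| 5% | −1.645 | 0.103 | 1.09–1.14 | 0.982–0.990 |
| 10% | −1.282 | 0.175 | 1.17–1.26 | 0.969–0.988 |
| 30% | −0.524 | 0.348 | 1.49–1.81 | 0.946–1.021 |

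For f = 30% and s = 0.8, dropping zeros gives exp(0.8 × 0.348/0.7) = 1.49. Simulation with n = 25 (200,000 runs) gave medians within 0.02 of these ratios.

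**Is that spread reasonable?** Protocol 5.1 admits "TBSA affected of between 2 and 30% at baseline", and Protocol 6.1.1 says "A pea-sized amount (approximately 250 mg) should cover approximately 2% BSA". That is 0.25 g per application at 2% and 0.25 × 15 = 3.75 g at 30%. If exposure is proportional to the amount applied, treated area alone gives a log-SD of ln 15/√12 = 0.78 for log-uniform TBSA, or 0.66 for uniform TBSA. Differences in absorption would add to this.

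**Sensitivity.** With a CV of 50–150% instead (s = √ln(1 + CV²), about 0.47–1.09), dropping zeros overstates by 5–13% at f = 5%, 10–24% at 10% and 46–138% at 50%. LLOQ/2 gives 0.85–1.09 times the truth over f = 5–50%. Its weak spot is low variability: at CV 50% and f = 30% it is exp(0.164 − 0.282) = 0.89, about 11% low, while dropping zeros there is 26% high.

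**Sampling time.** With applications as little as 8 hours apart, a Day 15 draw 4 hours after the morning dose complies but falls mid-interval. For the last visit, assume a 20:00 dose on Day 28 and an 08:00 draw. The sample is 12 hours after the dose on Day 29, and 12 + 72 = 84 hours after it on Day 32, the end of the window.

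**The case against.** The strongest reply is that the harm is small and visible. SAP 3.8 reports the number of assays above the LLOQ, so the share below it can be read off. The arithmetic mean, SD, CV, minimum and maximum all survive, and the median is standard under SAP 3.1. A geometric mean of zero or missing would be noticed. All of this stands and limits the importance of the point.

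The bias figures apply only if zeros are dropped, which the SAP does not prescribe. That is also correct: followed to the letter, the SAP gives no usable geometric mean, and the bias is the cost of the likely workaround.

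The rate and spread are assumptions, and the low absorption was seen with the 1% ointment, whereas this trial uses 2.75%. The error ranges do depend on them. The failure needs only one value below the LLOQ, and the upward direction of the bias does not depend on the spread.

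The unblinding argument is weak. Protocol 9.4.5 limits the PK summary to TER-101-treated subjects and no between-arm test is planned, so a late choice could not favour an arm. It remains a reason for tidiness, not a threat to inference. The separate PK report might carry its own convention, but none is cited.

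On sampling, 84 hours is an extreme under assumed clock times, and no half-life is given, so no effect on concentrations is shown. The time of last application is already recorded for each draw. The mismatch between label and sampling rule remains.

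**Conclusion.** The concern holds. As written, SAP 3.8 asks for a statistic that its own substitution rule makes zero or undefined as soon as one concentration at a visit is below the LLOQ, and no other section repairs this. With 25 active-arm samples, that is more likely than not once the true rate reaches 5%. The rate is unknown, so the likelihood is conditional; the algebra is not.

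The consequence is confined to one descriptive statistic for a secondary objective. Efficacy inference is untouched. It merits correction because the gap is certain on the text, plausible in practice and very cheap to close. The trough wording is a lesser, separate inconsistency that the same edit can settle.

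**What to change.** In SAP 3.8, keep zero for the arithmetic mean. Before unblinding, add one sentence giving a separate rule for the geometric mean: for example, substitute LLOQ/2, or report it as not calculated when more than a stated share of values is below the LLOQ. Show the number below the LLOQ beside it. LLOQ/2 is a convention whose accuracy depends on variability, so the share threshold should be stated with it.

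The same edit should confirm that the summary covers TER-101-treated subjects, as in Protocol 9.4.5. The PK analysis set in SAP 3.2.1 takes any safety-set subject with a draw, and vehicle samples, if assayed, would be nearly all zero.

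Separately, reconcile the trough label with the 4-hour sampling rule. Either present concentrations by time since last application, or reserve the label for samples meeting a definition fixed before unblinding.

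Cost: one SAP sentence for the geometric mean, and one SAP definition or a clarification of the protocol endpoint text for the trough label. No new data are needed, because the time of last application is already collected.

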3.9 INTERIM ANALYSES

There is no interim analysis planned for the study.

4 CHANGES TO PLANNED ANALYSES

Due to the small sample size of the study and the infrequent assessment of response over time, the Kaplan-Meier (KM) analysis of time to onset of response (EASI-75, EASI-50) will not be conducted.

Because the change from baseline in the IGA is expected to take on a limited set of values, it will be considered as ordinal data rather than a continuous variable, and thus will be analyzed using a generalized linear model for repeated ordinal data.

The change in individual components of EASI (erythema, edema/papulation, excoriation, lichenification) by visit will not be analyzed, only EASI by region will be analyzed due to limitation in defining EASI score for each sign/symptom.
